#### **Patient Enrollment**

Primary outcomes of blood pressure control are measured at the patient level for patients clustered within trainees as reported in the electronic medical record. Patients eligible for inclusion in the outcome analysis included being: 1. English-speaking; 2. Non-White racial/ethnic minority; 3. Medicaid recipient (regardless of race/ethnicity); 4. have hypertension. Exclusion criteria: We exclude patients with pregnancy, dementia, schizophrenia, bipolar illness, or other serious medical co-morbidity that would interfere with hypertension self-control, including enrollment in hospice. Secondary patient-reported outcomes of self-reported adherence and quality of communication with providers is measured from a subset of patients meeting the same eligibility criteria who are randomly recruited in periods before and after the training intervention.

### **Intervention Assignment and Recruitment**

The educational intervention was integrated into the residency programs in IM and FM, and into the curriculum for DNP students. We initially aimed to enroll entire specialty cohorts of IM, FM, and NP trainees over a 3-year period, with each academic year constituting an intervention cycle, with 3 cycles of implementation corresponding to 3 sequential academic years. Due to the COVID emergency, this was extended to 4 years of enrollment across 4 academic years. Within the first pre-COVID academic year, we randomized training times to 1 of 5 start dates using a stepped wedge design. Our biostatistician used a random sequence generator to assign 5 groups of learners, from within each program, to 1 of 5 staggered intervention training dates within an academic year.

**Version 3.0 updates:** Due to COVID, randomization to training times within each academic year was not possible. Each training program schedulers assigned the trainees according to availability within the learning schedules in order to maintain clinician availability to provide care during the COVID crisis. However, across all years, the program was delivered over two in-person sessions (and via virtual teleconferencing during COVID), scheduled five weeks apart, to leverage a spaced learning design.

The sessions were designed to minimize the time burden of the intervention on trainees outside of the classroom. As such, the in-person training sessions combined multiple educational components that trainees completed individually, but as part of an onsite group session. In each educational session, components included: “individual” online didactic modules, online IATs, face-to-face clinical practice simulation with SPs, and “group-based” facilitated debriefing sessions. Originally, training in skills to mitigate the effects of implicit bias detailed by Devine et

al. was addressed as part of the group-based IAT debriefings that preceded case simulations with SPs. Each of the two, in-person sessions lasted about four hours. If trainee participants were unable to attend one of the sessions due to scheduling conflicts, we provided alternative dates for attendance.

**Version 3.0 updates:** After the first year of the intervention and in response to feedback from learners and faculty and in light of growing awareness of the need to address learner defensiveness in implicit bias education, we re-designed subsequent the CONSULT educational program. Implicit bias and mitigating skills were updated and reframed based on strategies described by Cooper using the RELATE mnemonic: Respect, Empathize, Listen, Ask about your assumptions, Talk and Engage patients in problem solving (RELATE). Cooper's framework is grounded in what is known about effective communication between clinicians and patients of different racial and ethnic groups and in the Ladder of Inference of Argyris and Senge about how to interrupt unconscious processes that people follow to make decisions. Further theoretical grounding for the item domains was drawn from early evidence for bias mitigation skills proposed by Devine et al. These original strategies include: 1) individuation, which relies on preventing stereotypic inferences by obtaining specific information about group members and 2) perspective taking, which involves taking the first-person perspective in the individual with whom you are trying to communicate. RELATE does not retain two controversial elements of Devine's original strategies, including 'stereotype replacement', which involves replacing stereotypical responses for non-stereotypical responses, and 'counter-stereotypic imaging' which involves imagining a representative person that goes against a standardized mental picture that is held in common by members of a group and that represents an prejudiced attitude; these strategies are omitted because there is concern they inadvertently perpetuate negative stereotypes.

## **Outcome Measures and Data Collection**

### Trainee Measures

*Trainee Demographics.* We collect trainee age, gender, race/ethnicity, training year, whether they are US or foreign-born, and fluency in another language.

*Trainee IAT, Explicit Bias Measures, Bias Awareness, and Reaction to the IAT.* Trainees are asked to complete online Race/Ethnicity IATs [Black/White, Latino/White] and Race/Ethnicity-Medical Compliance IATs [Black/White, Latino/White]. Trainees were asked about their corresponding explicit beliefs and perceptions of what "other health professionals"

believe about race/ethnicity and race/ethnicity-related medical compliance in order to assess trainees' perception of their own bias as being "better than average". To assess trainees' reaction to the IAT, three questions are included from Howell & Ratliff using a 4-point scale (Strongly disagree, Disagree, Agree, Strongly Agree) to measure the trainees' degree of defensiveness to the IAT. Trainees also complete a 7-item Bias Awareness Scale, with items assessed on a 6-point scale (strongly agree to strongly disagree) and higher scores indicating greater bias awareness. In year 1, these items were collected online during each of the in-person training sessions and included 2 IATs at each session (total 4 IATs).

**Version 3.0 update:** After the first year of the intervention and in response to feedback from learners and faculty and in light of growing awareness of the need to address learner defensiveness in implicit bias education, we re-designed subsequent the CONSULT assessments to reduce the number of IATs requested, we made the IAT an optional component, and we requested completion of only one race-compliance IAT.

*Assessment of Trainees by SPs.* Community SPs complete standardized checklists of trainee performance measuring communication skills, perceptions of respect, emotional response, concern, empathy, listening skills, involvement in shared decision-making, engagement and partnership, BP measurement technique, and global performance. Standardized patient evaluators included simulation center standardized patient staff who participated in hypertension management clinical simulations with the trainees. Standardized patient evaluators were not limited in the number of trainees they could evaluate and provided ratings between September 2018-April 2022.

**Version 3.0 update:** The evaluation checklist was organized to reflect the RELATE framework.

#### Patient Measures

The primary trial outcome is the change in BP as reported in the EMR. Clinical measurements are collected in the 15-week control period prior to CONSULT-BP training period and during a 20-week post intervention period. The *main outcome* measures in the primary analysis will be systolic and diastolic BP (mm Hg) from the EMR. Analyses will stratify BP control as defined by the Joint National Commission 8: controlled HTN defined as SBP of <140/90 for most patients, or SBP < 150/90 for patients  $\geq 60$  years without a diagnosis of diabetes or chronic kidney disease, and uncontrolled hypertension as defined as greater than these values.

**Version 3.0 updates:** The original study design also included secondary patient self-reported outcomes including adherence to visits, diet modification and antihypertensive medication use as measured by the BP Self-Care Scale, Hypertension Medication Nonadherence Scale, and quality of communication and trust measured in the Health Care Climate Questionnaire and the trust sub-scale of the Primary Care Assessment Survey. In year 1, these surveys were administered in clinic offices of participating trainees in the 15-weeks before and 20-week after the educational intervention. This was not possible after the first year of the trial due to the COVID emergency.

## **Data Management**

We conducted data abstractions from the electronic medical record for primary outcomes assessment using a system that extracts data from the clinical database, reformats it and stores it on a separate analytics server to make querying the database more efficient and extract data without impacting clinical flow. Primary data collection from trainee self-report and patient questionnaires were entered into an electronic data capture system, RedCAP, using case report forms designed for this purpose, with the exception of the IATs which were directly collected by Project Implicit via an internet-based interface. Standardized patient assessments of trainee performance in the simulation lab are entered into the Learning Space data capture system used for all training and evaluation exercises at the clinical simulation lab.

## **Statistical analysis**

**Version 3.0 updates:** To maintain clinical staff services in the hospital, we were not able to maintain the cluster randomized stepped wedge design of training role out to all clinics and cohort during the COVID emergency. Therefore, we analyze these data as cohort study.

The first step of statistical analysis was examining the distribution of all data points to identify outliers or errors in the data of primary interest. Unadjusted analysis of categorical data was conducted with chi-square tests; analysis of continuous data used analysis of variance. Mixed effects regression models were fit to estimate the relative changes of clinical outcomes (BP values and clinical cut points) for patients seen by residents in the 6 months before and 6 months following the intervention periods. Mixed-effect linear regression models (logit models for normal and optimal BP categories) were fit with mixed effects for resident ID and for study cohort. All mixed-effect models also contained terms for the additional terms to account for study composition and potential confounders: study population (race and insurance strata),

clinical department (Family Medicine vs Medicine), age and sex, and relevant clinical comorbidity(diabetes, obesity, hyperlipidemia, coronary artery disease, cerebrovascular disease, and tobacco use). In order to determine if the study intervention was differentially effective for the different patient groups (ie. white patients with Medicaid and patients of color with either private insurance, Medicare, or Medicaid), we modeled interaction terms between 4-level population variable and intervention period. P-values less than 0.05 were considered statistically significant.

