### Objectives

The aims of the clinical trial are to evaluate the effect of this 3-part, training program on:

1. patient blood pressure outcomes, reported in the electronic medical record (EMR); 2. self-reported patient medication and diet adherence, as measured by the Hypertension Medication

Nonadherence Scale and the Blood Pressure Self-Care Scale; 3. patient-reported quality of provider communication, as measured by the Health Care Climate Questionnaire; 4. the trust sub-scale of the Primary Care Assessment Survey; and 5. trainee bias awareness, as measured by the Bias Awareness Scale.

**Version 3.0 updates:** Objectives 2-4 were not possible because the collection of patient self-reported data was precluded due to the COVID emergency.

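### A change-in-BP outcome is estimated by comparing patients seen before training with patients seen after it, with no patient-level term, so a shift in attendance can move the estimate either way

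*Combined protocol and SAP*

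**What the plan says.** Patient Measures sets the outcome: "The primary trial outcome is the change in BP as reported in the EMR". Statistical analysis estimates it with mixed models for BP "for patients seen by residents in the 6 months before and 6 months following the intervention periods". These models "were fit with mixed effects for resident ID and for study cohort", and no patient effect is named. They add "terms to account for study composition and potential confounders": race and insurance strata, department, age, sex, and a list that covers diabetes, obesity, hyperlipidaemia, coronary and cerebrovascular disease and tobacco use. Earlier BP, earlier attendance and new-patient status are not listed. No analysis compares who was seen in each period.

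On attendance, Patient Measures says the original design had "secondary patient self-reported outcomes including adherence to visits, diet modification and antihypertensive medication use". Of the surveys that carried these items it says: "This was not possible after the first year of the trial due to the COVID emergency". No EMR measure of attendance takes their place.

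The unit of analysis is not stated. Sample size calculation turns about 10 and 20 eligible patients per trainee into 205 × 10 = 2050 and 205 × 20 = 4100 observations, which implies one observation per patient per period. The windows also differ between sections: Patient Measures has "Clinical measurements are collected in the 15-week control period prior to CONSULT-BP training period and during a 20-week post intervention period", against six months on each side in Statistical analysis.

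**The concern.** An EMR reading exists only if the patient came. Patients seen after training need not be the patients seen before it. A resident effect compares the same resident in two periods, not the same patient. If relatively more patients with high BP attend afterwards, the post-training mean rises although nobody's BP changed, and a real benefit is hidden. If such patients drop out of view, a benefit appears that is not there.

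This is bias in the point estimate, so a larger sample does not reduce it. After year 1 the timing of training was no longer randomised and the data are analysed as a cohort study, so the design offers no protection against such shifts in the later years. With attendance unreported, a reader could not tell whether one had occurred.

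**Working it through.** **Benchmark.** The plan claims more than 90% power for 3 mmHg. It gives no SD or ICC, so the figure cannot be reproduced from its own inputs. With independent observations, 2050 v 4100 and two-sided 5%, power exceeds 90% for any SD up to 3 / [(1.960 + 1.282) × √(1/2050 + 1/4100)] = 34.2 mmHg. Here only the 3 mmHg target matters.

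**Inputs (all assumed).** Between-patient SD 14, within-patient SD 12, no true BP change, and Poisson visits averaging 1.2 before and 1.6 after (the ratio 0.75 equals 15/20 weeks). The log visit rate rises by b per between-patient SD. A patient 14 mmHg above average then has exp(0.1) = 1.11, exp(0.2) = 1.22 or exp(0.3) = 1.35 times the average patient's rate. No covariate adjustment is included.

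**Every reading enters.** The visit-weighted mean is displaced by 14 × b, so the spurious difference is 14 × (b_post − b_pre):
- 0.1 to 0.2: 14 × 0.1 = +1.4
- 0.2 to 0.1: −1.4
- 0.1 to 0.3: 14 × 0.2 = +2.8

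**One value per patient per window.** The chance of being seen is 1 − exp(−λ). To first order the mean of those seen is displaced by 14 × b × k(λ), with k = λ·exp(−λ) / [1 − exp(−λ)]. This gives k(1.2) = 0.517 and k(1.6) = 0.405.
- 0.1 to 0.2: 14 × (0.2 × 0.405 − 0.1 × 0.517) = +0.41
- 0.2 to 0.1: 14 × (0.1 × 0.405 − 0.2 × 0.517) = −0.88
- 0.1 to 0.3: 14 × (0.3 × 0.405 − 0.1 × 0.517) = +0.98

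Integrating over the normal distribution instead gives +0.39, −0.86 and +0.91. The asymmetry comes from the unequal visit rates. With six-month windows at the same weekly rate, λ = 1.2 × 26/15 = 2.08 on both sides and k = 0.297, which gives ±0.4 and +0.8.

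**Simulation of the same scenarios (mmHg):**

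| b before → after | Every reading | One value, no patient effect | One value, patient random effect | Seen in both windows |
|---|---|---|---|---|
| 0.1 → 0.2 | +1.4 | +0.4 | +0.2 | 0.0 |
| 0.2 → 0.1 | −1.4 | −0.9 | −0.3 | 0.0 |
| 0.1 → 0.3 | +2.8 | +0.9 | +0.4 | 0.0 |

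Keeping every reading and adding only a patient intercept gives +0.35, −0.34 and +0.67. The both-windows contrast is not always clean: if return depends on the observed pre-training reading, it is off by −0.2 to −0.4.

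**A second mechanism.** Suppose 40% of a panel are poor attenders running 10 mmHg higher, seen with probability 35% against 65% for the rest. Before training they form 0.4 × 0.35 / (0.4 × 0.35 + 0.6 × 0.65) = 26.4% of those seen. If their attendance rises to 45%, the share is 0.18/0.57 = 31.6%, a shift of 10 × 0.052 = 0.5 mmHg. At 55% and 65% the shares are 36.1% and 40.0%, giving 1.0 and 1.4. Simulating 205 residents with 30 patients each gave +0.5, +0.9 and +1.3, with a resident-only 5% test rejecting 17%, 51% and 91% of the time.

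**The case against.** **The size depends on a unit the plan does not state.** A reader might infer that every reading enters and quote 1.4 to 2.8 mmHg as the bias of the plan as written. The documents do not support that. Statistical analysis is silent on the unit, and Sample size calculation counts one observation per patient per period. On that unit the range is about 0.4 to 1.0. This part of the objection stands.

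**The programme was not shown to target attendance.** A reader might infer that it was meant to change visit-keeping, so that better engagement necessarily masks the BP effect. Objectives names only "self-reported patient medication and diet adherence". Visits appear once, as a self-reported secondary item of the original design. Masking also requires the added attenders to have higher BP, which nothing in the documents establishes. The direction is open.

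**Case mix is already addressed.** The covariates include comorbidities related to BP and may absorb part of the shift, and the simulations above ignore them. But none measures BP level or attendance. Patient Measures also plans stratification by BP control, without saying which reading defines the stratum, so it cannot be counted as a remedy.

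**The alternatives are imperfect.** A random patient effect mixes within-patient and between-patient information, so it is not a pure within-patient contrast, as its residual bias shows. Patients seen in both windows are selected on returning. Both points stand, and they argue against replacing the primary contrast with a paired one.

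**Conclusion.** The concern holds in a limited form. The outcome is a change, but the model compares two sets of attenders that may differ, with no patient effect, no term for earlier BP or attendance, and no report of who was seen. The resulting bias can take either sign.

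Its size cannot be derived from the documents, which give no SD, visit rate, return rate or link between BP and attendance. Under the assumed values and before covariate adjustment, it is about 0.4 to 1.0 mmHg with one value per patient per window (13% to 33% of the 3 mmHg target) and 1.4 to 2.8 mmHg (47% to 93%) if every reading enters. These figures show what modest shifts could do; they do not estimate what happened. Nothing here shows that attendance changed or that the primary result is wrong. The improvement is cheap and worth making.

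**What to change.** In Statistical analysis:

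1. State the unit. Use one BP value per patient per window, for example the mean of that window's readings, and add a patient random effect alongside resident and cohort. In the scenarios above this brings the bias to about 0.2 to 0.4 mmHg; say that it does not remove it. The two descriptions of the windows must be reconciled first, since the value per window depends on them.
2. Add a sensitivity analysis of within-patient change in patients seen in both windows, noting that this group is selected on returning and is subject to regression to the mean.
3. Report from the EMR, by period, visits per eligible patient, the share of pre-window patients who return, and the pre-window BP of those who do and do not return.

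**Cost.** SAP wording and re-aggregation of EMR data already held. Collapsing repeat readings loses some information; how much cannot be judged without the visit counts. Setting says data collection ran to December 2022, and Statistical analysis describes the models as already fitted. The revised analysis must therefore be labelled post hoc and presented beside the existing model, not in place of it.

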## METHODS AND ANALYSIS

### Trial Design

This was originally designed as a cluster randomized trial of the CONSULT-BP training using a stepped wedge design to evaluate the effectiveness of one-time CONSULT-BP training on patient outcomes. The original rationale for the stepped wedge design accommodates pre-existing training schedules to mitigate the effect of temporal trends in clinical skill proficiency. Within cohorts of internal medicine residents, family medicine residents, and nurse practitioner students, groups of trainees were intended to be randomly assigned to 1 of 5 training time start dates in a given academic year using a stepped wedge design to accommodate pre-existing training schedules and mitigate the effect of temporal trends in clinical skill proficiency. It also allows for all trainees to be assigned to the intervention, which was a pre-condition of involvement by the participating training programs, in order to meet training requirements. This design is statistically advantageous because all trainees have control and intervention periods, everyone serves as their own control, allowing for within and across participant comparisons based on data collection both before and after the intervention. Our model randomizes training times to one of five start dates within each academic year to accommodate pre-existing training schedules and to mitigate the effect of temporal trends in clinical skill proficiency.

**Version 3.0 updates:** The cluster randomized trial design was not feasible beyond the first year of our study because our study was paused during the COVID emergency. To maintain clinical staff services in the hospital, we were not able to maintain the randomization of training within year because the needs of the training program's provision of clinical services took precedent over the didactic training. Therefore, we analyze these data as cohort study.

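### The before/after BP models list no time term, so time change within a trainee that the patient covariates do not explain is counted as training effect

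*Combined protocol and SAP*

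**What the plan says.** Under Statistical analysis, BP is compared "for patients seen by residents in the 6 months before and 6 months following the intervention periods". The models "were fit with mixed effects for resident ID and for study cohort". The section then states: "All mixed-effect models also contained terms for the additional terms to account for study composition and potential confounders". The terms it goes on to name are race/insurance stratum, department, age, sex and a set of comorbidities. Intervention period enters as the exposure and in an interaction with the population variable. Study cohort is not defined.

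Patient Measures gives different windows: "Clinical measurements are collected in the 15-week control period prior to CONSULT-BP training period and during a 20-week post intervention period".

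Trial Design explains that randomised start dates were chosen to "mitigate the effect of temporal trends in clinical skill proficiency". The Version 3.0 update there says "we were not able to maintain the randomization of training within year". Intervention Assignment and Recruitment confirms the split. For year 1: "Within the first pre-COVID academic year, we randomized training times to 1 of 5 start dates using a stepped wedge design". Afterwards: "Each training program schedulers assigned the trainees according to availability within the learning schedules". The data are now analysed as a cohort study. All trainees were to receive the training, so there is no never-trained group.

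**The concern.** For every trainee, the after window is later than the before window in both calendar time and clinical experience, and the study spans the COVID emergency. The plan itself identified temporal trends as a threat and met it by design. Most of that design protection has gone, and no section puts a modelling step in its place.

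Staggered starts also do not remove a trend from a before/after contrast by themselves. They help only if the model uses calendar time, so that trained and untrained trainees are compared in the same period. Without such a term, drift in BP, trainee maturation or a COVID-related change in care can create, enlarge or hide an effect in the primary outcome. The reader would have no means of telling which.

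**Working it through.** **1. Can the listed terms absorb time?** A resident term is constant across a trainee's two windows. A cohort term is too, whether cohort means specialty group or academic year of training. Both remove differences in level between trainees or cohorts, not change within a trainee. The exception is a cohort term coded by visit date, which would act as a coarse time term; the section does not say this was done. The patient covariates absorb changes in case mix. What is left is residual time change.

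**2. The plan's own figure.** The Sample size calculation gives 205 trainees with 10 readings before and 20 after (2050 and 4100), and >90% power for 3 mmHg. No SD or ICC is given, so the figure cannot be reproduced exactly. For independent readings:
- SE = SD × √(1/2050 + 1/4100) = 0.02705 × SD.
- 90% power holds for SD up to 3 / (3.24 × 0.02705) ≈ 34.2 mmHg.
- For the uncontrolled subgroup (1025 and 2050) the limit is about 24.2 mmHg.

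The claim is therefore plausible for a model without time adjustment.

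**3. Bias per unit of trend.** Assume readings are spread evenly over each window and that the five weeks between the two sessions lie between the windows. Bias = trend × distance between window midpoints.
- 6-month windows: 26/2 + 5 + 26/2 = 31 weeks; 31/52.18 = 0.594 mmHg per 1 mmHg/year.
- 15/20-week windows: 15/2 + 5 + 20/2 = 22.5 weeks; 22.5/52.18 = 0.431 mmHg per 1 mmHg/year.

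Without the five-week gap the factors would be 26/52.18 = 0.50 and 17.5/52.18 = 0.34. To mimic the full 3 mmHg, the trend would have to be 3/0.594 ≈ 5.0 or 3/0.431 ≈ 7.0 mmHg/year.

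**4. False-positive rate.** Assume SD 20, ICC 0.01, a resident random intercept and 10/20 readings for 205 trainees.
- SE = 20 × √0.99 × 0.02705 = 0.538.
- Rate = P(|N(bias/SE, 1)| > 1.96).

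| Residual trend | 6-month windows: bias, rate | 15/20-week windows: bias, rate |
|---|---|---|
| 1 mmHg/year | 0.59, 20% | 0.43, 13% |
| 2 mmHg/year | 1.19, 60% | 0.86, 36% |

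These trends are illustrations; the documents give none.

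**5. Season.** In a simulation with five starts seven weeks apart, a seasonal swing of 2 mmHg amplitude moved the estimate by only 0.13 to 0.27 mmHg. With a single start date it moved it by about 1.5 mmHg. The spread of start dates after year 1 is not documented.

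**6. Precision after adjustment.** Same assumptions, 15/20-week windows, four cohorts, five equal start groups per cohort, and 5-week period effects within cohort. Power for 3 mmHg = Φ(3/SE − 1.96).

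| Model | SE | Power |
|---|---|---|
| No time term | 0.54 | >99% |
| Time-adjusted, between-trainee information used, starts 10 to 5 weeks apart | 0.72–1.02 | 99–84% |
| Time-adjusted, within-trainee information only, starts 5 to 10 weeks apart | about 1.25–1.36 | 67–60% |

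Bunched starts are worse. Across the reading counts examined, and with between-trainee information used, five starts spanning 12 weeks give an SE of 1.3–1.6 (power 63–49%). If all starts fall within five weeks, the effect cannot be estimated.

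**The case against.** The case on the other side has four parts.

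- **The list is loosely worded.** A time term may have been fitted and not reported, or study cohort may have been coded by date. This stands as a limit on certainty: what is certain is the omission from the text, not the content of the fitted model.
- **The change of design is disclosed.** Several sections give the loss of randomisation and its cause, and no section claims randomised evidence for the later years. That is true, but disclosing a cohort analysis neither adjusts for time nor tells the reader that time is unadjusted.
- **The bias may be small.** Case-mix change is adjusted for, season may largely average out, and a trend of 5 to 7 mmHg/year is needed to imitate the full target effect. This also stands. A reader might infer that all before/after change is attributed to training, or that false-positive rates of 87% or more apply. The first ignores the listed covariates. The second requires 26/26 readings per trainee (205 × 52 = 10,660 in total) against the planned 6,150, as well as an assumed trend.
- **The remedy is itself imperfect.** After year 1 the comparison of trained with untrained trainees in the same period rests on dates set by schedulers, and a calendar term cannot fully separate training from differing trainee experience. This stands, and it must be stated beside any adjusted estimate. It limits what adjustment can show; it does not make the unadjusted estimate safer.

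**Conclusion.** The point holds for residual time change and should be resolved before the primary BP estimate is interpreted as an effect of training. As written, the model adds 0.59 or 0.43 mmHg to the estimate for each 1 mmHg/year of trend that the covariates do not explain, in whichever direction the trend runs. That arithmetic rests only on the documents' windows, the placing of the five-week gap and evenly spread readings.

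The false-positive rates, SEs and power figures rest in addition on an assumed SD of 20, an assumed ICC of 0.01, all 205 planned trainees, and readings that are independent apart from the trainee effect. They are neither bounds nor estimates of what happened. A reader might conclude that any BP improvement found is spurious. The documents do not support that: they give no trend, and the bias could equally hide a true effect.

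**What to change.** 1. In Statistical analysis, define study cohort and list every time term that was fitted. If there was none, add calendar-period effects (month or 5-week block within academic year) to the mixed models. Label them post hoc, because the models are described as already fitted.
2. Before that, tabulate trained and untrained readings by calendar period within each cohort. Where they overlap, report the time-adjusted estimate. State that after year 1 it depends on scheduler-set, non-random dates and does not fully separate training from differences in trainee experience. Where they do not overlap, limit the conclusion to an uncontrolled before/after association.
3. Reconcile the 15/20-week and 6-month windows, since they set the size of the bias. Restate power for the time-adjusted model.

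The work is a revision of the text, a table and a re-run on data already extracted. The real cost is precision: on the assumptions above, the SE rises from 0.54 to between 0.72 and about 1.36, depending on start spacing and on whether between-trainee comparisons are used. The loss is larger if starts were bunched, so the >90% power statement may not hold and should not be carried over unchanged.
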